15.4 Phone Interview: 24 Hour Diet Recalls

Within 24 hours after patient registration, study staff must FAX the **S1600** Telephone Contact Form to the Exercise, Diet, Genitourinary, & Endocrinology (EDGE) Research Laboratory at [name]. Phone the EDGE lab at [name] to ensure the FAX was

received. After registration prior to beginning the study nutrition therapy and again around 30 days after surgery, nutrition staff from the EDGE Research Laboratory will interview the patient over the phone to obtain two 24-hour dietary recalls (one weekday and closest weekend day) at each time point. The interview is conducted over the phone so that nutrition staff may be able to clarify ambiguities with the patient and ensure data collection completeness. Each phone interview will take approximately 15 minutes. 24-hour food recalls will be analyzed with Nutrition Data System for Research (NDSR). Energy, macronutrients, fish oil, and amino acid intake will be summarized and reported to control for the background diet.

Note: If the patient is having their visit locally at EDGE, the phone interview can be conducted during the patient's visit.

16.0 ETHICAL AND REGULATORY CONSIDERATIONS

The following must be observed to comply with Food and Drug Administration regulations for the conduct and monitoring of clinical investigations; they also represent sound research practice:

Informed Consent

The principles of informed consent are described by Federal Regulatory Guidelines (Federal Register Vol. 82, No. 12, January 19, 2017) and the Office for Protection from Research Risks Reports: Protection of Human Subjects (Code of Federal Regulations 45 CFR 46). They must be followed to comply with FDA regulations for the conduct and monitoring of clinical investigations.

Institutional Review

This study must be approved by an appropriate institutional review committee as defined by Federal Regulatory Guidelines (Ref. Federal Register Vol. 82, No. 12, January 19, 2017) and the Office for Protection from Research Risks Reports: Protection of Human Subjects (Code of Federal Regulations 45 CFR 46).

Monitoring

This study will be monitored by the Clinical Data Update System (CDUS) Version 3.0. Cumulative CDUS data will be submitted quarterly to CTEP by electronic means. Reports are due January 31, April 30, July 31 and October 31.

Confidentiality

Please note that the information contained in this protocol is considered confidential and should not be used or shared beyond the purposes of completing protocol requirements until or unless additional permission is obtained.

16.1 Adverse Event Reporting Requirements

a. Purpose

Adverse event data collection and reporting, which are required as part of every clinical trial, are done to ensure the safety of patients enrolled in the studies as well as those who will enroll in future studies using similar agents. Adverse events are reported in a routine manner at scheduled times during a trial. (Directions for routine reporting are provided in [Section 14.0](#).) Additionally, certain adverse events must be reported in an expedited manner to allow for more timely monitoring of

patient safety and care. The following guidelines prescribe expedited adverse event reporting for this protocol.

b. Reporting method

This study requires that expedited adverse events be reported to SWOG Operations Office using the Cancer Therapy Evaluation Program Adverse Event Reporting System (CTEP-AERS). CTEP's guidelines for CTEP-AERS can be found at <http://ctep.cancer.gov>

c. When to report an event in an expedited manner

When the adverse event requires expedited reporting, submit the report within 10 calendar days of learning of the event as specified in [Table 16.1](#).

In the rare event when Internet connectivity is disrupted notification is made to SWOG by telephone at [contact] or by email [contact]. An electronic report MUST be submitted immediately upon re-establishment of internet connection.

d. Other recipients of adverse event reports

The SWOG Operations Office will forward reports and documentation to the appropriate regulatory agencies and drug companies as required.

Adverse events determined to be reportable to the Institutional Review Board responsible for oversight of the patient must be reported according to local policy and procedures.

e. Expedited reporting for commercial agents

Commercial reporting requirements are provided in [Table 16.1](#). The commercial agent(s) used are Impact Advanced Recovery and Oral Nutrition Control Drink. If there is any question about the reportability of an adverse event or if Internet connectivity is disrupted please telephone or email the SAE Program Manager at the Operations Office, [name] or [contact] before preparing the report.

NOTE: For this study, all adverse events requiring expedited reporting must initially be reported on the Adverse Event Form in the appropriated Treatment Cycle folder in Medidata Rave. Once the adverse event is entered into RAVE, the Rules Engine will confirm whether or not the adverse event requires expedited reporting. The CTEP-AERS report must then be initiated directly from the Adverse Event Form in Medidata Rave. Do not initiate the CTEP-AERS report via the CTEP-AERS website. Sites are encouraged to confirm the Expedited Reporting Evaluation Recommendation with the reporting criteria outlined in [Table 16.1](#).

Table 16.1. Expedited reporting requirements for adverse events experienced by patients on Blinded Nutritional Drink within 30 days of the last administration of the commercial agent(s), Impact Advanced Recovery and Oral Nutrition Control Drink.

ATTRIBUTION	Grade 4		Grade 5 ^a	
	Unexpected	Expected	Unexpected	Expected
Unrelated or Unlikely			CTEP-AERS	CTEP-AERS
Possible, Probable, Definite	CTEP-AERS		CTEP-AERS	CTEP-AERS
CTEP-AERS: Indicates an expedited report is to be submitted via CTEP-AERS within 10 calendar days of learning of the event ^b .				

^a This includes all deaths within 30 days of the last dose of treatment with a commercial agent(s), regardless of attribution. Any death that occurs more than 30 days after the last dose of treatment with a commercial agent(s) and is attributed (possibly, probably, or definitely) to the agent(s) and is not due to cancer recurrence must be reported according to the instructions above.

^b Submission of the on-line CTEP-AERS report plus any necessary amendments generally completes the reporting requirements. You may, however, be asked to submit supporting clinical data to the Operations Office in order to complete the evaluation of the event. If requested, the specified data should be sent within 5 calendar days by fax to [contact].

f. Reporting Pregnancy, Pregnancy Loss, and Death Neonatal

1. **Pregnancy:** Study participants who become pregnant while on study; that pregnancy should be reported in an expedited manner via CTEP-AERS as **Grade 3 “Pregnancy, puerperium and perinatal conditions – Other (pregnancy)”** under the **Pregnancy, puerperium and perinatal conditions SOC**.

Additionally, the pregnancy outcome for patients on study should be reported via CTEP-AERS at the time the outcome becomes known, accompanied by the same Pregnancy Report Form used for the initial report.

2. **Pregnancy Loss:** Pregnancy loss is defined in CTCAE as “Death in utero.” Pregnancy loss should be reported expeditiously as **Grade 4 “Pregnancy loss”** under the **Pregnancy, puerperium and perinatal conditions SOC**.

A Pregnancy loss should **NOT** be reported as a Grade 5 event under the Pregnancy, puerperium and perinatal conditions SOC, as currently CTEP-AERS recognizes this event as a patient death.

3. **Death Neonatal:** "Death neonatal is defined in CTCAE as "Newborn death occurring during the first 28 days after birth." A neonatal death should be reported expeditiously as **Grade 4 "Death neonatal"** under the **General disorders and administration SOC**.

Neonatal death should **NOT** be reported as a Grade 5 event under the General disorders and administration SOC as currently CTEP-AERS recognizes this event as a patient death.

NOTE: When submitting CTEP-AERS reports for "Pregnancy", "Pregnancy loss", or "Neonatal loss", the Pregnancy Information Form should also be completed and faxed with any additional medical information to [contact]. The potential risk of exposure of the fetus to the investigational agent(s) or chemotherapy agent(s) should be documented in the "Description of Event" section of the CTEP-AERS report.

The Pregnancy Information Form is available at:
http://ctep.cancer.gov/protocolDevelopment/adverse_effects.htm

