7.4 Treatment: Postoperatively

Agent	Dose	Route	Schedule
Blinded Nutrition Drink	3 bottles daily (178 mL per bottle)	oral	For 5 days after Radical Cystectomy surgery; between meals

a. After surgery, patients consume 3 blinded bottles daily (178 mL per bottle) of nutrition drink between meals as a supplement to their regular diet for 5 days after surgery, to be administered by the nurse or dietitian. The study staff will deliver the patient's 15 bottles of blinded nutrition drink to the surgical unit (for accessibility to the patient prior to their 24 hours post-surgery time point), along with study staff contact information, a copy of the **S1600** protocol (for the surgical unit's reference), and a copy of the **S1600** Patient Intake Calendar – After Surgery. Study staff should label each bottle with the patient's hospital ID (in addition to the study labeling already included per [Section 3.0](#)) to ensure the bottles are administered to the correct patient. Study staff will instruct the patient's nurse or dietitian to keep the bottles refrigerated until dispensed so that the drinks are served cold. The patient should return their **S1600** Patient Intake Calendar – Before Surgery on the day of surgery, so study staff should coordinate with the surgical unit to collect this form.

b. Patients should resume intake within 24 hours after surgery. If resumption of diet is delayed, patients will resume the study drink once they can tolerate it (within 24-72 hours after surgery per protocol recommendation). Every effort should be made to have the patient begin post-operative consumption of the study nutrition drinks within at most 72 hours after surgery, though the patient should still consume the drinks even if resumption of diet is delayed more than 72 hours after surgery. Patient will consume the drinks for five days, regardless of what day diet is

resumed. Nurse or dietitian in the unit will initiate post-operative feeding once the physician order with approval to start the study drink is charted in the participant's medical record.

- c. Postoperative Oral Nutrition Therapy Considerations:
 - 1. Start with lower volumes and increase as tolerated to give 178 ml 3 times a day.
 - 2. Educate patient to take the drink very slowly in increments over the course of 2-4 hours or longer. Study drink must be kept chilled.
 - 3. Encourage patient to walk around the unit before taking a second small dose.

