 - 4. If patient feels too bloated, nauseous, or exhibits excessive burping, or hiccuping, then it is permissible to stop and wait for several hours before trying another feeding.
 - 5. Patient can receive other food (e.g., regular diet) if allowed by the surgeon, but minimize sugary drinks or foods (sodas, juices, gelatin).
- d. The study staff are responsible for getting the remainder of patient-specific study product (15 drink bottles) to the post-op unit for the nurse or dietitian there to dispense to the patient starting the day following surgery as described in [Section 7.3a](#). If the patient is discharged from the hospital before consuming all 5-day supply of study product, the remaining should be sent home with instructions to continue until all are consumed.
- e. If patient consented to participating in specimen banking, provide the patient with the kit for stool sample collection for first bowel movement after hospital discharge per [Section 15.2](#).

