14.4 Data Submission Overview and Timepoints

Please reference the ORP Manual on the CRA Workbench (www.swog.org) for detailed General Forms and Guidelines, as well as some disease-specific and study-specific forms. There are also many other chapters available in the manual to be used for regular reference of SWOG processes and procedures.

a. WITHIN 24 HOURS AFTER REGISTRATION:

FAX the **S1600** Telephone Contact Form directly to the EDGE Research Laboratory at [name] per form instructions. Phone the EDGE lab at [name] to ensure the FAX was received.

b. WITHIN 7 DAYS AFTER REGISTRATION:

Submit the following:

S1600 Onstudy Form

S1600 Nutrition Status Form

S1600 Wong-Baker Pain Scale

Scored Patient-Generated Subjective Global Assessment (PG-SGA)*

Pathology report from TURBT*

*NOTE: Include all TURBT reports within the last two years including the report with the primary diagnosis. Upload reports via the Source Documentation: Baseline form in Rave®.

c. PRIOR TO BEGINNING PREOPERATIVE TREATMENT, AT DAY 2 AFTER CYSTECTOMY, AND AT DAY 30 ± 7 DAYS AFTER CYSTECTOMY:

Collect, process, and submit specimens as outlined in [Section 15](#).

d. WITHIN 14 DAYS AFTER PREOPERATIVE TREATMENT:

Submit the following:

S1600 Treatment Form

S1600 Adverse Event Form

S1600 Laboratory Values Form

S1600 FAACT form

S1600 Cover Sheet for Patient-Completed Questionnaires

S1600 Body Composition Form

Scan Report from DXA*

Laboratory report including CBC with differential*

*NOTE: Upload the DXA scan report via the Source Documentation: Baseline form in Rave®. Upload lab results via the Source Documentation: Lab folder in Rave.

e. **WITHIN 14 DAYS AFTER CYSTECTOMY:**

Submit the following:

S1600 Cystectomy Form

Operative report from cystectomy*

Pathology report from cystectomy*

*NOTE: Upload reports via the Source Documentation: Follow Up form in Rave®.

f. **IF PATIENT DOES NOT UNDERGO CYSTECTOMY, WITHIN 14 DAYS AFTER PLANNED CYSTECTOMY DATE:**

Submit the **S1600** Off Protocol Notice.

g. **WITHIN 14 DAYS AFTER POSTOPERATIVE TREATMENT:**

Submit the following:

S1600 Adverse Event Form

S1600 Wong-Baker Pain Scale

S1600 Laboratory Values Form

Laboratory report including CBC with differential*

*NOTE: Upload lab reports via the Source Documentation: Lab form in Rave®.

h. **WITHIN 14 DAYS AFTER 30-DAY POSTOPERATIVE ASSESSMENT:**

Submit the following:

S1600 30-Day Post-Op Assessment Form**

S1600 Treatment Form

S1600 Adverse Event Form

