S1600 Laboratory Values Form

S1600 Nutrition Status Form

Scored Patient-Generated Subjective Global Assessment (PG-SGA)*

S1600 FAACT form

S1600 Cover Sheet for Patient-Completed Questionnaires

S1600 Body Composition Form

S1600 Wong-Baker Pain Scale

Scan Report from DXA*

Laboratory report including CBC with differential*

*NOTE: Upload the PG-SGA and DXA scan reports via the Source Documentation: Follow Up form in Rave®. Upload lab reports via the Source Documentation: Lab form in Rave®.

**NOTE: This form must be both submitted electronically, and the completed version signed (paper or electronically) by the surgeon uploaded via the Source Documentation: Follow Up form in Rave®.

i. WITHIN 14 DAYS AFTER 90-DAY POSTOPERATIVE ASSESSMENT:

Submit the following:

S1600 90-Day Post-Op Assessment Form**

S1600 Off Protocol Notice

**NOTE: This form must be both submitted electronically and the completed version signed (paper or electronically) by the surgeon uploaded via the Source Documentation: Follow Up form in Rave®.

j. AT 3 MONTHS, 6 MONTHS, 9 MONTHS, 12 MONTHS, 18 MONTHS, 24 MONTHS, AND 36 MONTHS AFTER CYSTECTOMY OR UNTIL DEATH:

Submit the SWOG Follow Up Form.

k. WITHIN 4 WEEKS OF KNOWLEDGE OF DEATH:

Submit the Notice of Death.

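### The last scheduled Adverse Event Form follows the Day 30 visit counted from surgery, but the 30-day expedited window counts from the last drink and usually closes some days later

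*Combined protocol and SAP*

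**What the plan says.** The protocol runs adverse event reporting on two clocks.

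**Expedited reporting, counted from the last drink.** The title of Table 16.1 (Section 16.1e) reads "Expedited reporting requirements for adverse events experienced by patients on Blinded Nutritional Drink within 30 days of the last administration of the commercial agent(s". In that window the table asks for unexpected Grade 4 events that are at least possibly related, and for all Grade 5 events. The note above the table says that "all adverse events requiring expedited reporting must initially be reported on the Adverse Event Form" in Rave, and the CTEP-AERS report is started from there. Section 16.1c allows 10 calendar days once the site knows of the event.

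**Routine reporting, counted from the treatment periods and from surgery.** Section 16.1a says that routine reports come at scheduled times and points to Section 14.0. Section 14.4 lists the S1600 Adverse Event Form three times: after preoperative treatment (14.4d), after postoperative treatment (14.4g), and "WITHIN 14 DAYS AFTER 30-DAY POSTOPERATIVE ASSESSMENT" (14.4h). Sections 7.7 and 9.0 place that assessment at Day 30 ± 7 after surgery. The next list, "WITHIN 14 DAYS AFTER 90-DAY POSTOPERATIVE ASSESSMENT" (14.4i), contains the 90-Day Post-Op Assessment Form and the Off Protocol Notice, but no Adverse Event Form. Neither 14.4 nor 16.1 says when routine collection ends.

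**What fixes the last-drink date.** Section 7.4b says "Patient will consume the drinks for five days, regardless of what day diet is" resumed. It aims for a start within 72 hours at most, "though the patient should still consume the drinks even if resumption of diet is delayed more than 72 hours after surgery". Section 7.4d says that if the patient is discharged with bottles left, "the remaining should be sent home with instructions to continue until all are consumed".

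**The concern.** The period in which the plan treats an event as potentially drink-related for expedited purposes is anchored to one date, and the schedule that prompts sites to look for events is anchored to another. If the first period ends after the last scheduled form, its final days rely on a site happening to hear of an event.

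Two things are at stake. First, the expedited duty starts only when the site knows of the event, so an unexpected, possibly related Grade 4 event after the Day 30 visit is found passively. Second, an event in those days that does not qualify for expedited reporting has no scheduled form at all. The exposed stretch is longest for patients who resume feeding late, and a feeding delay of five days or more is itself a listed complication (ileus, Section 10.2a).

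**Working it through.** The plan states no closing day for the window, so there is no figure of its own to reproduce. The check is day arithmetic with surgery as Day 0.

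**Inputs**
- Window length: 30 days after the last drink (Table 16.1).
- Postoperative drinking: five days from the day intake resumes (Section 7.4b).
- Start day: Day 1 (study calendar, Section 9.0), Day 3 (72 hours, Section 7.4b), or Day 5. Day 5 is an illustrative late start taken from the ileus definition in Section 10.2a. It is allowed because Section 7.4b sets no upper limit.
- Visit with the last scheduled form: Day 23 to Day 37 (Section 9.0, footnote J).

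**Formulas**
- Last drink = start day + 4.
- Window closes = last drink + 30.
- Days left after the visit = max(0, window close − visit day).

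**Results**

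| Start | Last drink | Window closes | Left after Day 23 visit | Left after Day 30 visit | Left after Day 37 visit |
|---|---|---|---|---|---|
| Day 1 | 1 + 4 = Day 5 | 5 + 30 = Day 35 | 12 | 5 | 0 |
| Day 3 | 3 + 4 = Day 7 | 7 + 30 = Day 37 | 14 | 7 | 0 |
| Day 5 | 5 + 4 = Day 9 | 9 + 30 = Day 39 | 16 | 9 | 2 |

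As a share of the 30-day window, a Day 30 visit leaves 5/30 = 17% to 9/30 = 30%, and a Day 23 visit leaves 12/30 = 40% to 16/30 = 53%.

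**Variants**
- Counted in elapsed time, a start at 72 hours plus 120 hours of drinking ends on Day 8, and the window closes on Day 38 instead of Day 37.
- Slower intake, or leftovers taken at home under Section 7.4d, moves the close later. No upper bound is given.
- A patient who takes no postoperative drinks had the last one on Day −1. The window closes on −1 + 30 = Day 29, and a Day 30 visit covers it.

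**Does another scheduled item fill the days after the visit?** The Day 90 visit (Section 7.8) calls for Clavien-Dindo grading of surgical complications. Toxicity is graded by CTCAE 5.0 (Section 8.1), and Table 16.1 turns on attribution and expectedness. Section 7.8 does not ask for either. Readmissions up to Day 90 are recorded with a reason (Section 10.2e), and deaths prompt a Notice of Death (Section 14.4k). These routes reach the serious events, but not as CTCAE grade with attribution to the drink.

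**The case against.** The strongest reply is that routine and expedited reporting are separate systems. The Table 16.1 window governs only the expedited one, which is driven by the event and not by a visit. A site that hears of a qualifying event on Day 36 must enter it on the Adverse Event Form and report it, whatever Section 14.4 schedules. Nothing requires routine forms to span the expedited window. This stands. A reader might infer from the schedule that the last days of the window have no adverse event collection; the documents do not support that. A serious event in those days first learned of at Day 90 would also still start the 10-day clock.

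Second, the Day 30 form is not due until 14 days after the visit. After a Day 30 visit that reaches Day 44, beyond every close in the table; after a Day 23 visit it reaches Day 37. The form might therefore pick up later events. But the 14 days are a submission deadline, and the plan does not state the period that the form covers. The possibility stays open and is not a safeguard.

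Third, the fields of the forms are not shown, and the plan defers some scheduling rules to group guidelines and a manual that are outside the documents. The 90-day form may ask for more than Section 7.8 says. Likewise, the lack of an adverse event row in Section 9.0 proves little, since the three forms that are scheduled have no row there either.

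Fourth, the drinks are medical foods taken for ten days, and the effects named in Section 8.2 are mild gastrointestinal ones. This bears on severity, and it is a fair reason to keep the point small.

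**Conclusion.** The mismatch is confirmed, in a limited form. For patients who complete five postoperative days starting on Day 1, 3 or 5, the expedited window outlasts a Day 30 visit by 5 to 9 days. This includes the ordinary patient on the calendar's own schedule. The range is 12 to 16 days for a Day 23 visit and 0 to 2 for a Day 37 visit. In those days no scheduled CTCAE or attribution form prompts the site, and non-expedited events have no scheduled form.

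Two further inferences should be resisted. The last drink is not always on Day 5 or later: patients who never resume drinking took their last one before surgery. Nor is their Day 29 close a mismatch in the other direction, since a Day 30 visit covers it and Section 7.10 requires follow-up and forms even after early discontinuation.

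The conclusion assumes calendar-day counting and that the Day 30 form covers events up to the visit, a period that the plan leaves unstated. The documents give no event rate for these days, so the number of events missed cannot be estimated, and under-counting is a possibility, not a demonstrated result. The primary endpoint is unaffected. Severity is minor: this is a cheap improvement.

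**What to change.** 1. Add the S1600 Adverse Event Form to Section 14.4i, for events with onset after the Day 30 visit and up to 30 days after the last drink.
2. Make the last-drink date available in the database. The After Surgery intake calendar already records a date for each drinking day, but Section 7.5 tells sites not to submit calendars, and the fields of the Treatment Form are not shown.
3. State in Sections 14.4 and 16.1 that routine collection ends at the later of the Day 30 visit and 30 days after the last drink.
4. Reconcile the five-day period in Section 7.4b with the open-ended home use in Section 7.4d. At three bottles daily, 15 bottles last 15/3 = 5 days, so the two agree when intake is full and can differ when it is not. The last-drink date sets the window, so the passages need one reading; which one is for the study team.

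The cost is one existing form at an existing visit and a few lines of text, with no new visit or sample. The downside is some data entry and long recall. With the Day 90 visit on Day 83 to 97, and events from just after a Day 23 visit up to a Day 39 close, recall runs from 83 − 39 = 44 days to just under 97 − 23 = 74 days.
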